Clinical Study Protocol

Protocol Number: HBCOVID03

“A Randomized, Placebo-Controlled, Double-Blind, Efficacy and Safety Study of Allogeneic HB-adMSCs for the treatment of COVID-19”

IND Number:	19718
NCT Number	NCT04362189
Name of Product	Allogeneic HB-adMSCs Hope Biosciences Adipose Derived Mesenchymal Stem Cells
Phase of development	II
Indication	Coronavirus Disease (COVID-19)
Sponsor Contact	[name] Director of Research Hope Biosciences Stem Cell Foundation [name] [contact] [contact] [contact]
Protocol Version	1.6
Protocol Version Date	15-JUN--2020

-CONFIDENTIAL-

This document and its contents are the property of and confidential to Hope Biosciences. Any unauthorized copying or use of this document is prohibited.

Ethics and Regulatory Compliance Statement

The procedures set forth in this protocol are designed to ensure that the Hope Biosciences Stem Cell Foundation and principal investigator(s) abide by the International Conference on Harmonization (ICH) current Good Clinical Practice (cGCP) guidelines, current Good Laboratory Practice (cGLP) guidelines, the Declaration of Helsinki, and applicable local regulatory requirements and laws in the conduct, evaluation, and documentation of this study.

1. Synopsis

Title of the Study:	“A Randomized, Placebo-Controlled, Double-Blind, Efficacy and Safety Study of Allogeneic HB-adMSCs for the treatment of COVID-19”
Protocol Number:	HBCOVID03
Investigators	HBCOVID03-01 Principal Investigator: [name] Co-Investigator: [name] HBCOVID03-02 Principal Investigator: [name] Co-Investigator: [name]
Study Site(s):	HBCOVID03-01 River Oaks Hospital and Clinics [name] HBCOVID03-02 United Memorial Medical Center [name]
Phase of development	II
Objectives	
Primary:
 
 - To investigate the safety and efficacy of HB-adMSCs in the treatment of patients with COVID-19 by decreasing inflammation, improving oxygenation, and decreasing time to return to room air (RTRA) 
Secondary:
 
 - To investigate the safety and efficacy of HB-adMSCs in improving clinical status of patients suspected to have COVID-19

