Patients will receive four intravenous infusions of 100 million HB-adMSCs throughout the entire duration of the study.

Arm 2 (placebo) (n=40)

Patients will receive four intravenous infusions of placebo (saline solution) throughout the entire duration of the study.

Safety assessments will be ongoing. Safety tests will include EKG, Complete Blood Count with differential, Complete Metabolic Profile (to include renal function and hepatic function) and Coagulation Panel screening for hepatotoxicity, cytopenias, renal failure or alterations in the coagulation cascade that might entail a safety concern for the individual. Efficacy will be measured by change from baseline in inflammatory markers (IL-6, CRP, IL-10, TNF-alpha), change from baseline in oxygenation, and time to receive negative PCR test result, change from baseline in exploratory markers (D-dimer, myoglobin, troponin, creatinine kinase, serum ferritin, CD3CD56, CD4/CD8, VEGF), time to return to room air (RTRA), change from baseline chest x-ray, change from baseline CT scan, and change from baseline in 7-point ordinal scale.

Selection and Withdrawal of Patients

Inclusion Criteria

1. Men, and women, over 18 years of age inclusively.
2. Suspected COVID-19 infection
3. Provides consent or consent is given by their legally authorized representative (LAR)
4. Agrees to the collection of venous blood per protocol.

Exclusion Criteria:

1. Pregnancy, lactation and those who are not pregnant but do not take effective contraceptive measures, in women of childbearing age.
2. Patients who have participated or are participating in a clinical trial of an experimental vaccine for SARS-CoV-2 or coronavirus during the study or within 30 days.
3. Inability to provide informed consent or to comply with test requirements.

4. Any medical disease or condition that, in the opinion of the site Principal Investigator or sub-investigator, precludes study participation. Including acute, subacute, intermittent or chronic medical disease or condition that would place the subject at an unacceptable risk of injury, render the subject unable to meet the requirements of the protocol, or may interfere with the evaluation of responses or the subject's successful completion of this trial.

Withdrawal, Removal, and Replacement of Patients

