Allogeneic HB-adMSCs, from a single qualified donor, is to be administered as an IV infusion. Each syringe will be provided by Hope Biosciences on the day of the infusion after all quality control essays have been performed and the results are within normal range.

Instructions for Administration

The designated study staff will administer the investigational product in the following manner:

- Prior to administration, visually inspect the infusion solution for particulates. If foreign particles are present, do not use the solution.
- Emergency equipment, such as epinephrine, antihistamines, and corticosteroids must be available in the event of infusion-related reactions.
- Start IV administration after dilution.
- Administer the infusion solution over a period of 1h. Observe the patient for at least 1-hour post-infusion for acute infusion-related reactions, including anaphylaxis. Continual monitoring will resume, with hospital staff observing vital signs, including blood pressure, pulse, or signs of rash/hives. Acute increase or decrease (30-40 mm/Hg from pre-infusion level) in blood pressure, an elevation of more than 20 BPM from baseline, or appearance of rash/hives would warrant review by PI.
- See Appendix 1 for guidelines on diagnosing anaphylaxis.
- Do not store or reuse any unused portion of the infusion solution. Any unused product or waste material should be disposed.
- Volume of study drug infused, start times, and stop times will be recorded. If any portion of the infusion (cell solution) is discarded, the reason will be recorded in the CRF.
- The patient will be monitored for a total of 2 hours from drug exposure to discharge.
 - a. During the Investigational product administration (1 hour) vital signs will be measured at minute 0, 15, 30 and 45.
 - b. Post infusion, vital signs will be measured at minute 0, 30, and 60.

Investigational Product Assignment (Randomization and Blinding)

Randomization

A total of 100 eligible subjects will be randomized to either placebo or treatment group within the associated study arm at baseline. Randomization will determine whether the subject receives placebo or HB-adMSCs.

A neutral, third-party personnel will be responsible for assigning the participants' treatment group. This role will be referred to as 'randomizer'. The designated personnel from the drug manufacturer will be responsible in labeling and packaging the investigational product for each

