participant. This role will be referred to as ‘mixer’. Participants’ names are not disclosed to the mixer and the unblinded information will only be known to the randomizer. Is with knowledge of bag contents will be the designated mixer.

Blinding for Clinical Evaluators

To minimize assessment bias, clinical evaluators (data analysts and physicians) will be trained on how to maintain blinding to treatment as best as possible. “Best as possible” means that blinding will be maintained unless an adverse event occurs that requires unblinding the physician, which is determined by the medical monitor or DSMB. Training includes review of the process of blinding, describing who will be responsible for assigning product for the appropriate group, labels that will be used to identify subjects but not treatment group, and the process that should be followed if an adverse event occurs, triggering review by medical monitor and/or DSMB.

Planned Unblinding

Unblinding of patient information will only occur in the case of adverse event suspected to be related to the investigational product, per the medical monitor and DSMB.

Regulatory authorities and/or the IRB may request the unblinding of data from one or more patients at any time.

Investigational Product Assignment and Infusion Schedule (Staggering)

Each patient will be allocated a unique subject number at screening and will retain this number throughout the study.

The Investigational Product is to be administered to all eligible, enrolled patients in Arm 1.1 and Arm 2.1 by intravenous infusion at a dose of 1×10^8 cells at days 0, 3, 7, and 10. Every effort should be made to adhere to the dosing schedule. However, a scheduled infusion should not be administered if a patient has an ongoing AE that, in the Investigator’s opinion, warrants holding the infusion.

Prior and concomitant conditions

The investigators should document all prior significant medical history. Additional conditions present at the time when informed consent is given and up to the time of first infusion (Day 0) are to be regarded as concomitant conditions. Illnesses first occurring or detected during the study and/or worsening of a concomitant condition during the study should be documented as AEs in the CRF. The exception is that results from COVID-19 testing will be added to the CRF as part of medical history.

Prior and concomitant medications

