## 2.2. Study Design

Overview of Study Design and Key Features	
Randomized, double-blind, placebo-controlled, parallel group study	
Design Features	

• Randomized, double-blind, Placebo controlled study.

• 100 Subjects

• 2 Treatment groups

▪ Group 1 → HB- adMSCs

▪ Group 2 → Placebo

• Duration of treatment: up to 7 days, and overall study includes screening (up to 7 weeks prior to randomisation), and 4 treatment visits after randomisation scheduled at Infusion 1 (Day 0), Infusion 2 (Day 3), Infusion 3 (Day 7), and Infusion 4 (Day 10). Follow-up at day 28 (EOS).

Dosing	

• HB- adMSCs (Hope Biosciences adipose derived mesenchymal stem cells) is to be administered as an IV infusion with a dose of 100 million cells

• Placebo is to be administered as an IV infusion. Contains Saline solution 0.9%

Treatment Assignment	

• Participants will be randomised 3:2 to receive HB-adMSCs active treatment or Placebo.

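### Study staff must look into every infusion, cells in one arm and saline in the other, yet no masking of product appearance or separation from outcome assessment is described

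*Protocol*

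**What the plan says.** The title of the protocol is "A Randomized, Placebo-Controlled, Double-Blind, Efficacy and Safety Study of Allogeneic HB-adMSCs for the treatment of COVID-19". The Investigational Plan sets out the arms. For Arm 1 (n=60): "Patients will receive four intravenous infusions of 100 million HB-adMSCs throughout the entire duration of the study". For Arm 2 (n=40): "Patients will receive four intravenous infusions of placebo (saline solution) throughout the entire duration of the study". SAP section 2.2 specifies the placebo as 0.9% saline.

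Under Instructions for Administration, the designated study staff are told: "Prior to administration, visually inspect the infusion solution for particulates". A solution with foreign particles must not be used. The same list says "Start IV administration after dilution", without saying who dilutes or where, and the infusion then runs for one hour.

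The concealment that is described stands under Randomization and Blinding for Clinical Evaluators:

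- A neutral third party (the randomizer) assigns treatment.
- A person from the manufacturer (the mixer) labels and packages the product without knowing participants' names.
- Data analysts and physicians are trained to stay blinded. The training covers "labels that will be used to identify subjects but not treatment group".

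Knowledge of the contents is limited first to the randomizer, then in the next sentence to the mixer as well.

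**The concern.** A particulate check only works if the person doing it can see the fluid. One fluid is a cell suspension and the other plain saline, so the check may show the arm to someone whom the Randomization section does not list among those who know it. Labels and third-party allocation conceal the assignment on paper; they do nothing about what the fluid looks like.

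Several outcomes depend on judgement at the site. Time to return to room air depends on when supplemental oxygen is stopped, and saturation readings depend on how much oxygen is being given. The ordinal scale separates patients with and without limitation on activities. Adverse event causality is a medical judgement. Holding an infusion is left to the Investigator's opinion, and it also affects who is analysed: the efficacy set (protocol, Analysis Population; SAP section 4) contains only patients who received all four infusions.

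**Working it through.** The plan gives no figure on this point to reproduce. The check sets the provisions side by side and counts the exposure.

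**1. Does the inspection apply to both arms?** Yes. Instructions for Administration makes no exception by arm.

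**2. Who is meant to know the contents?** The randomizer and the mixer (Randomization). The staff who inspect and administer are neither, and are not named in Blinding for Clinical Evaluators, which covers data analysts and physicians.

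**3. Is appearance masked?** Neither document mentions a matched placebo appearance, an opaque bag, syringe or sleeve, a covered line, or a check on whether the blind held. Neither refers to a pharmacy manual that might supply this. The protocol explains what maintaining the blind as well as possible means only through an exception for adverse events, so loss through appearance is not considered.

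**4. Are inspectors kept apart from assessors?** No such separation is stated. Nor is it stated that they are the same people.

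**5. In what form does the product reach the site?** Details of the investigational product speaks of a syringe; Randomization speaks of a bag. With dilution unassigned, it is unclear whether site staff also handle the undiluted product.

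**6. How often, and when?** Arm sizes come from the Investigational Plan, with four infusions each:

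- HB-adMSCs: 60 × 4 = 240 inspections
- Placebo: 40 × 4 = 160 inspections
- Total: 240 + 160 = 400

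The first for every patient is on Day 0, before any post-baseline efficacy assessment.

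**7. Would the fluids look different?** The documents give neither appearance nor planned volume. Taking 50 to 500 mL purely as an assumption, the cell concentration would be 100 million ÷ 50 = 2.0 million per mL down to 100 million ÷ 500 = 0.2 million per mL, against zero in saline. Whether that can be seen is neither confirmed nor excluded.

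**8. Which primary measures are exposed?** Study Endpoints lists six: TNF-alpha, IL-10, IL-6, C-reactive protein, oxygenation and time to return to room air. The first four are laboratory values, little open to observer judgement. The last two are exposed.

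**The case against.** The strongest reply is that the central fact is assumed: nothing says how either product looks, so what is shown is an unspecified masking method and not a broken blind. That stands. A reader might infer that the blind is certainly lost, or that the trial has no masking at all. The documents support neither. Labels are neutral, allocation is by a third party, and the mixer does not know names.

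A second reply is that the inspecting staff need not be the people who judge outcomes; causality and holding decisions belong to the investigator, and physicians are to be kept blinded. This also stands in part. The documents do not equate the two groups, but they do not separate them either, and that separation is what would protect the endpoints.

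Third, dilution may well be done before release, as the mixer's title suggests. The text leaves this open, so site dilution cannot be counted as an established exposure.

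A reader might also see a clue to the arm in the CRF instruction: "If any portion of the infusion (cell solution) is discarded, the reason will be recorded in the CRF". It is not one. The wording is the same for every patient, so it cannot distinguish the arms.

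Finally, a reader might want a figure for the false effect on time to return to room air. That would need the share of patients starting on oxygen, the number of days by which knowledge of the arm shifts weaning, and an efficacy threshold. The documents give none of these. The 95% and 75% posterior probabilities in SAP sections 5.1 and 7.1.4.1 concern baseline comparability.

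**Conclusion.** The concern holds in a conditional form. A procedure written into the protocol works against the protocol's own limit on who knows the contents, and nothing described offsets it. If the fluids can be distinguished by eye, following the plan as written can reveal the arm from Day 0, with up to 400 planned occasions. That condition is an assumption.

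The exposure is uneven: two of the six primary measures, plus the ordinal scale, adverse event causality and infusion-holding decisions, and through the last of these, entry to the efficacy set. The size of any resulting bias cannot be stated from the documents. This should be fixed: analysis cannot restore a blind once it is lost, and prevention costs little.

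**What to change.** Amend Instructions for Administration and the randomization and blinding sections of the protocol:

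- **Inspection and covering.** Keep the particulate inspection. Have it and any dilution done out of sight of evaluators, by the mixer or by a designated handler among existing staff. Then cover every bag or syringe and its line, in both arms, with an identical opaque sleeve before it reaches the bedside.
- **Roles.** State that anyone who sees the uncovered product does not decide or record oxygen status, the ordinal scale, adverse event causality or the holding of infusions.
- **Handling.** Reconcile the syringe with the bag, and state who dilutes.

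The cost is sleeves and line covers, a short amendment and some constraint on staff assignment at the site. If infusions are already complete, the study report should say who saw the uncovered product and how the blind was kept.

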A Data Safety Monitoring Board (DSMB), consisting of three individuals appointed by a third-party contractor, will meet as scheduled by this protocol to review safety throughout study conduct. Specifically, the DSMB will meet to assess the progress of the first five patients with mild symptoms after their second infusion, and a decision on continuation of study will be made prior to the third infusion (day 7). The same will occur for the first five patients experiencing severe symptoms after their second infusion, and a decision on continuation of study will be made prior to their third infusion (day 14). All other patients may be screened beforehand so that enrollment may occur once the committee declares it may resume. DSMB is scheduled for at least 3 meetings pertaining to this protocol: after the mild symptom group receives their second infusion, after the severe symptom group receives their second infusion, and at study midpoint. Additional meetings may be necessary, upon request from the Medical Monitor.

DSMB will review all deaths (to assure non-attribution), cases of anaphylaxis or suspected anaphylaxis, thromboembolic events, new malignancy/tumor, infections/hospitalizations (including unrelated to COVID-19 but due to underlying condition). DSMB will also review safety data at mid-point of the study.

Risks

Potential Risks of the Investigational Product and Clinical Investigation

Risks Associated with HB-adMSCs

Respiratory Risks:

A potential risk is that the infusion could initiate a VTE event with subsequent

cardiopulmonary sequelae of respiratory failure and/or right heart strain/failure. We plan to monitor oxygen saturation, and respiratory rate/work of breathing for the first 2 hours post-infusion. The patient will be examined for VTE events (clinical exam, oxygen saturation) during each infusion visit and at each follow-up visit.

Hepatic Risks:

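### The unblinding rule, read literally, leaves the DSMB without safety data by arm at its sentinel and midpoint reviews

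*Protocol*

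**What the plan says.** **Who holds the codes.** The protocol's Randomization section says that "the unblinded information will only be known to the randomizer". The next sentence, garbled in the text, adds a second role: "Is with knowledge of bag contents will be the designated mixer". The mixer is not told participants' names.

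**When codes are opened.** Planned Unblinding says that "Unblinding of patient information will only occur in the case of adverse event suspected to be related to the investigational product", with the medical monitor and DSMB deciding. It then makes one exception: "Regulatory authorities and/or the IRB may request the unblinding of data from one or more patients at any time". The DSMB is not included in it.

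**What the DSMB reviews.** The Data Safety Monitoring Board section says that "the DSMB will meet to assess the progress of the first five patients with mild symptoms after their second infusion", and then: "The same will occur for the first five patients experiencing severe symptoms after their second infusion". A decision on continuing follows each. A third scheduled meeting comes later: "DSMB will also review safety data at mid-point of the study". The board also looks at every death and at listed event types, including thromboembolic events, without a relatedness filter. The section does not mention tables by arm, masked A/B tables or an unblinded statistician.

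**Stopping rules.** In Study Stopping Rules, rule 2 acts on three or more of the same Grade 3 or higher event and specifies neither arm nor causality. Rule 5 acts on a Grade 4-5 event that the medical safety monitor and/or DSMB links in time to an HB-adMSC infusion.

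**Allocation.** SAP 2.2: "Participants will be randomised 3:2 to receive HB-adMSCs active treatment or Placebo". The SAP describes analyses for the clinical study report after database lock (1 and 3.1) and plans no DSMB output.

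**The concern.** The unblinding rule is circular for a group signal. The board learns a patient's arm only once an event is suspected to be related to the product. When single cases look like the disease, an imbalance between arms is what would raise that suspicion.

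The documents themselves describe the overlap. The Risks section names venous thromboembolism leading to respiratory failure and right heart strain as a product risk. The Introduction lists ARDS and acute heart injury among the common complications of COVID-19. The causality scale calls an event unrelated when another cause is the most plausible one. An excess of such events on HB-adMSCs could therefore build up from cases that are each reasonably put down to the infection.

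The sentinel reviews raise a further question. They govern whether dosing and enrolment continue, yet they count patients, not patients given cells. The board is not told how much exposure to the product lies behind its decision.

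**Working it through.** **Inputs.** From the documents: 100 patients, arms of 60 and 40, allocation 3:2, sentinel groups of five. Assumed: midpoint means 50 patients split 30:20, independent allocation, and all event rates (the documents give none).

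**Stated split.** 100 × 3/5 = 60 and 100 × 2/5 = 40, as the protocol gives. The total of 100 rests on anticipated demand, so there is no power figure or detection threshold to reproduce.

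**Midpoint, pooled.** Pooled rate = 0.6 × p(active) + 0.4 × p(placebo). A pooled 22% can arise from:
- 22% in both arms
- 30% v 10%: 0.6 × 0.30 + 0.4 × 0.10 = 0.22
- 36.7% v 0%: 0.22 / 0.6 = 0.367

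In counts, 10 events among 50 patients fits each of these splits (one-sided Fisher exact test):

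| Active | Placebo | p |
|---|---|---|
| 6/30 (20%) | 4/20 (20%) | 0.65 |
| 8/30 (27%) | 2/20 (10%) | 0.14 |
| 9/30 (30%) | 1/20 (5%) | 0.031 |
| 10/30 (33%) | 0/20 (0%) | 0.003 |

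Pooled data cannot tell the first row from the last.

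**Sentinel groups.** Number treated ~ Binomial(5, 0.6), mean 3.
- P(0) = 0.010, P(1) = 0.077, P(2) = 0.230, so P(2 or fewer) = 0.317. Drawing from exactly 60/40 gives 0.314.
- At least one of the two groups with two or fewer: 1 − (1 − 0.317)² = 0.534.
- With no events in n treated patients, the one-sided 95% upper bound on the event rate is 1 − 0.05^(1/n): 45% for n = 5, 63% for n = 3 and 78% for n = 2.

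**Rule 2 on pooled patients, no drug effect.** P(three or more of the same Grade 3+ event in 50) is 8%, 46% and 89% at background rates of 2%, 5% and 10%. The rule can bring a cluster to the board, but in a sick population it will often do so without any drug effect. The board then needs the split by arm to interpret what it sees.

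**What data by arm would add at midpoint.** Exact power, 30 v 20, one-sided Fisher at 0.025:

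| Placebo | Active | Power |
|---|---|---|
| 10% | 30% | 27% |
| 10% | 40% | 57% |
| 20% | 40% | 22% |
| 20% | 50% | 47% |

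**The case against.** **Pooled review is not stated.** A reader might infer that the protocol prescribes pooled DSMB data. It does not. The DSMB section is silent on format, no charter is among the documents, and the evaluators to be kept blind are data analysts and physicians, not the board. The unblinding rule could also be read as covering individual code-breaks only. This stands as a limit on the claim. But the rule is worded as exclusive and lists regulators and the IRB as its exception, so anyone following it literally would withhold data by arm from the board.

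**Unrelated events are not locked away.** A reader might infer that once an investigator calls an event unrelated, its code stays closed. Suspicion is judged by the medical monitor and DSMB, the board sees all deaths and listed events, and a marked AST/ALT rise within 72 hours is classed as infusion related by rule. This answers the concern for single striking cases, but not for an excess of events that each look like COVID-19.

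**A signal need not wait for the end.** A reader might infer that an imbalance would surface only at the final analysis, after 100 patients had been exposed. Only 60 are planned for HB-adMSCs, rules 2 and 5 can act earlier, and the protocol allows the sponsor interim looks at safety data. Those looks are optional and not stated to be by arm.

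**Rule 5 concerns timing.** Timing after an infusion can be judged blind. Whether that infusion contained cells cannot, and the rule names HB-adMSCs.

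**Codes may not settle much.** Five patients cannot show a difference between arms with or without codes, and midpoint power is modest. Even 6/30 v 1/20 gives a one-sided p of about 0.14. This stands, and it limits what the fix can promise.

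**Conclusion.** The concern holds as a gap in safety oversight. The protocol provides the DSMB with no safety data by arm at its three scheduled reviews, and its unblinding rule, read literally, excludes such data. An imbalance as large as 10/30 v 0/20 would look the same to the board as 6/30 v 4/20. Rule 5 asks about an HB-adMSC infusion that the board has no stated means of confirming.

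For the sentinel reviews the defect is unknown exposure, not a lost comparison. There is about a 32% chance per group that two or fewer of the five were treated, assuming independent 3:2 allocation. SAP 5.4.1 lists illness severity among five stratification factors and no block size is given, so the true figure may differ. A block of five filled within one stratum would give exactly three treated; patients spread over several strata would come closer to the binomial figure.

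The documents do not support the inference that access by arm would reliably detect harm. Its value is that large imbalances become visible.

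**What to change.** 1. Amend Planned Unblinding so that the DSMB is a standing exception. At each sentinel meeting and at midpoint it receives a closed report by arm from the existing third-party randomizer. The report covers AEs, SAEs, deaths, thromboembolic events and hepatic events, regardless of assigned causality. Sponsor and sites stay blinded.
2. Have each sentinel report state how many of the five patients received HB-adMSCs. Leave the sentinel count as it is: requiring five treated patients would move each review to about 5/0.6 = 8.3 randomised patients and would change a safety gate.
3. Reconcile the Randomization, Planned Unblinding, Study Stopping Rules and Data Safety Monitoring Board sections. The text should say who holds codes (randomizer and mixer), what level of blinding the board works under, and how rule 5 is judged when treatment is masked.

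The cost is a few sentences of protocol text, some added reporting work for a role that already exists, and a small extra risk that codes leak.
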